
Following the initial meeting with the PI, the participants will wear the sleep tracker on their wrist during the day and night for 4 weeks. The sleep tracker will monitor the physiological markers of sleep provided by wearable technology on sleep efficiency, time in bed, time actually sleeping, sleep midpoint, and time spent at each stage of sleep. Within the first week of participating in the study, student researcher(s) will contact the participant and perform a short 5- minute qualitative interview on the participants understanding and comprehension of the educational video along with a satisfaction survey (using a 5-point Likert scale). At the end of

the 4-week study period, the PI and/or student researcher(s) will once again meet with each participant. The participant will complete the following questionnaires once again: Sleep diary, Epworth Sleepiness Scale, Pittsburgh Sleep Quality Index, Sleep Hygiene Index, Perceived Stress Scale, Numeric Pain Rating Scale, and Patient Specific Functional Scale. Acceptability will be again assessed using a satisfaction survey (5-point Likert scale) and qualitative interview. Anthropometric data collection and vital signs will be reassessed, and the sleep tracker will be returned to the PI. Pre/post measurements will be compared and data analyses will be conducted using a 2x2 mixed factorial repeated measures ANOVA test. The PI will be assisted in the stats process by her mentor, [name] along with her peer in the psychology department at her university.

[figure not shown]
During the first year of this study, when in the treatment development phase, our primary outcomes for feasibility will be the following: recruitment (people enrolled from people contacted), retention and attrition (participants who complete the study and number who drop out), adherence (number of sessions attended and adherence to intervention protocol). Acceptability will be assessed using the satisfaction survey (5-point Likert scale) and qualitative interview. This information will be used to tailor the intervention to CDOA to further assess treatment effect in year two and three.

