Assessing overall sleep health is relatively new and therefore there is no established gold standard, however the Ru-SATED questionnaire (Table 1) has been shown to be a reliable and valid measure of sleep health.[35] We will use this in combination of objective data from the FitBit device to measure sleep health. Each sleep health domain will be dichotomized using the cut-off points in Table 1 with 0 = poor sleep health and 1 = good sleep health. The domains will be summed to create the composite sleep health score ranging from 0 - 6 with a higher score indicating better sleep health.

Sleep health domain	Source	Operational definition	Cut-off for good sleep health
Regularity	FitBit	Standard deviation of sleep midpoint, which is calculated as [sleep onset + (wake time – sleep onset/2)]	<60 min
Satisfaction	Sleep Diary	The sleep diary includes an item to rate “restedness upon awakening” with 0 = “not at all”, 1 = “somewhat”, 2= “moderately”, 3 = “quite a bit”, and 4 = “extremely”. Satisfaction will be operationalized as the average “restedness” score	Average of ≥3
Alertness	Epworth Sleepiness Scale	Epworth Sleepiness Scale which consists of 8-items of various activities (ie. sitting and reading, watching TV, etc) answered using a 4-point Likert Scale with 0 = “would never nod off” to 3 = “high chance of nodding off”	≤10
Timing	FitBit	Average sleep midpoint	2am-4am

Efficiency	FitBit	Average total minutes of sleep divided by time in bed multiplied by 100	>85%
Duration	FitBit	Average total minutes of sleep	6-8 hours

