**Figure 2: Study design for Specific Aim 2.**

Day	Daily Text
1 & 16	Go to sleep and wake up at the same time every day. This will help set your natural biological clock.
2 & 17	Exposure to bright natural light when you first wake up is also helpful to set your natural biological clock.
3 & 18	Use your bed for only sleep and sexual activity to help train your brain that if you are in your bed, you should be sleeping. Do not eat, work, or watch TV in bed. Do these activities outside of the bedroom.
4 & 19	Leave bed if unable to fall asleep within 20 minutes and return when sleepy. If unable to leave the bed due to limited mobility or safety concerns, do something relaxing (ie, relaxation techniques) until sleepy and able to fall to sleep.
5 & 20	Develop a relaxing bedtime routine. This may include taking a warm bath, reading a book, meditation, or stretching. Avoid stimulating activities right before bedtime, including watching TV or discussing a stressful topic.
6 & 21	Avoid moderate to vigorous exercise at least 2-3 hours before bedtime. Exercising immediately before bedtime stimulates your body and brain, making it hard to fall asleep. There is evidence however that doing regular (preferably moderate to vigorous) exercise improves your sleep at night. Talk to your physical therapist about an appropriate exercise program.
7 & 22	Avoid caffeinated foods and drinks at least 4 hours before bedtime (includes most tea, coffee, chocolate, and soft drinks). Check the presence of caffeine in your drink or food by reading the label. Caffeine can cause difficulty falling asleep and increase the number of times you wake up during the night.
8 & 23	Refrain from drinking alcohol or smoking at least 3 to 4 hours before bedtime. Although people may think drinking alcohol causes relaxation before bedtime it can actually increase the number of times you wake up during the night and can cause you to wake up early. Nicotine in cigarettes acts as a stimulant that can cause difficulty falling asleep.
9 & 24	Do not take unprescribed or over-the-counter sleeping pills.
10 & 25	Avoid daytime napping so that you are tired at night and can fall asleep easily. If you feel you need to take a nap, limit the nap to 30 minutes and avoid napping in the evening.

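### Raw mean midpoint and minutes asleep have no benefit direction under Table 1's two-sided windows, and Regularity, which the intervention targets first, is used only as a 0/1 flag

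*Combined protocol and SAP*

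**What the plan says.** **Scoring (Specific Aim 1, text before Table 1).** "Each sleep health domain will be dichotomized using the cut-off points in Table 1", with 0 for poor and 1 for good. "The domains will be summed to create the composite sleep health score ranging from 0 - 6".

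**Domain definitions (Table 1).**
- Timing: "Average sleep midpoint", good if 2am-4am.
- Duration: "Average total minutes of sleep", good if 6-8 hours.
- Regularity: "Standard deviation of sleep midpoint, which is calculated as" a formula in onset and wake time, good if <60 min.

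**Tracker markers (Specific Aim 1, Rationale and Experimental design).** The list is "sleep efficiency, time in bed, time actually sleeping, sleep midpoint, and time spent at each stage of sleep". The SD of midpoint is not on it.

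**Analysis (Specific Aim 1, Experimental design).** Pre/post measurements are compared with a 2x2 mixed repeated-measures ANOVA. No outcome-by-outcome list is given, and no score measures how far a value lies from a Table 1 window.

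**What the intervention targets.** A consistent bedtime and wake time is the first topic listed for the video. It is also the first text message (Table 2, days 1 and 16): "Go to sleep and wake up at the same time every day".

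**The concern.** Timing and Duration are two-sided by the plan's own definition. An earlier midpoint is an improvement for someone at 4:30 and a deterioration for someone at 2:10. More sleep is an improvement at 5.5 hours but not at 8.5. A mean of such values has no better direction, so a statistically significant shift in mean midpoint or minutes could be read as benefit or harm without support from Table 1. A null result could also hide improvement on both sides of the window.

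The flags have the right direction but are coarse. A rise from 5.0 to 5.9 hours (54 minutes) scores nothing, and a rise from 5.9 to 6.0 hours (6 minutes) scores a full point.

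Regularity is one-sided, so a lower SD is better throughout and nothing stands in the way of analysing it as a continuous measure. As planned it exists only as a flag, so the behaviour the intervention addresses first has no continuous tracker outcome.

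**Working it through.** **1. The plan's own figure.** Recruitment: 80 / (1 - 0.20) = 100, which reproduces. The 80 comes from the sizes of earlier studies. The plan gives no effect size, power or baseline distribution for any domain, so everything below rests on stated assumptions. Tests are two-sided at 0.05 (assumed). Arm sizes are 40 (80 / 2) and, where shown, 15 (printed in Figure 2).

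**2. Cancellation is possible, not certain.** Midpoints of 1:30 and 4:30 move to 2:30 and 3:30. The changes are +60 and -60 min, with mean 0, yet both flags go from 0 to 1.

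Simulated power on change scores, 40 per arm. Assumed: midpoint SD 1.2 h, duration SD 1.1 h, noise 0.25 h; people outside the window move 25% or 50% of the way to its centre.

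| Setting | Shift | Raw mean | Flag | Distance outside window |
|---|---|---|---|---|
| Timing centred at 3am | 25% | 0.06 | 0.17 | 0.73 |
| Timing centred at 3am | 50% | 0.05 | 0.66 | 0.95 |
| Timing centred at 4am | 25% | 0.68 | 0.20 | 0.94 |
| Timing centred at 4am | 50% | 0.96 | 0.79 | 1.00 |
| Duration centred at 7 h | 25% | 0.05 | 0.18 | 0.64 |
| Duration centred at 7 h | 50% | 0.04 | 0.64 | 0.88 |
| Duration centred at 6 h | 25% | 0.67 | 0.19 | 0.92 |
| Duration centred at 6 h | 50% | 0.96 | 0.81 | 1.00 |

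Cancellation is complete only when the sample is centred on the window. The flag loses most of the signal for small shifts and keeps most of it for large ones. Two cautions apply. The distance score is zero for everyone inside the window (45-64% of true values here), so it needs a suitable method. Change scores also assume a tracker value before the intervention, whereas the plan has the tracker worn only after the initial visit.

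**3. The ranking depends on the kind of movement.** Assume midpoints normal around 3am with SD 75 min, 40 per arm.
- Everyone moves 30% toward 3am, so the SD becomes 0.7 x 75 = 52.5 min. The share inside the window goes from 2Φ(60/75) - 1 = 58% to 2Φ(60/52.5) - 1 = 75%. Power: raw mean 5%, flag 37%, absolute distance from 3am 53%.
- Only people within 45 min of the window move, to just inside it. Power: raw mean 5%, flag 74-76%, distance from 3am 10%.

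**4. Regularity.** Assume the SD of midpoint is lognormal with log-SD 0.4 and median 45 to 75 min.

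*General 20% fall.* On the log scale the effect is |ln 0.8| = 0.223, or 0.223 / 0.4 = 0.558 standard deviations.
- 40 per arm: 0.558 x √(40/2) = 2.495, power about 69%.
- 15 per arm: 0.558 x √(15/2) = 1.528, power about 31%.

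The share under 60 min is Φ(ln(60/median)/0.4):

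| Median | Before | After (median x 0.8) |
|---|---|---|
| 45 min | 76% | 90% |
| 60 min | 50% | 71% |
| 75 min | 29% | 50% |

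Simulated flag power is 38-51% with 40 per arm and 15-22% with 15 per arm.

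*Change limited to people just over the cut-off.* Let only those at 60-75 min move, to 59 min. Because 0.8 x 75 = 60, the flag shares and the flag's power are the same as above. The mean log SD now falls by only 0.016 to 0.028, and simulated log-scale power drops to 5-7% at either arm size. The flag does better here.

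**The case against.** The strongest reply is that the plan already handles the two-sided windows. The flag has the right direction, does not cancel and follows Table 1 exactly. The document cites the underlying questionnaire as reliable and valid. First-year primary outcomes are feasibility measures. Sleep efficiency is already a listed continuous marker, and the Epworth scale is already repeated at four weeks. All of that stands, and it is why the composite should stay and no change is needed for those two domains.

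A reader might infer three stronger things that the documents do not support.
- *That movement into the window is lost.* It is what the flag records. What is lost is movement that crosses no cut-off.
- *That the raw means will cancel, or that the plan commits to testing them.* Cancellation needs people on both sides of a window, and no baseline distribution is given. Testing of raw midpoint and minutes is inferred from the marker list together with the ANOVA sentence; it is not stated.
- *That distance from 3am or from 7 hours would be the better score.* Table 1 treats every value inside a window as equally good. Such a score would count a move from 3:00 to 2:10 as 50 minutes of deterioration although both are good, and step 3 shows it can do far worse than the flag.

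The reply leaves two gaps open: no rule prevents a benefit or harm reading of the raw means, and Regularity has no continuous outcome.

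**Conclusion.** The point holds as a low-cost improvement to the sleep outcomes. It does not touch the first-year feasibility outcomes.

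That raw mean midpoint and minutes lack a benefit direction follows from Table 1 alone and needs no assumption. How much they cancel depends on where participants start: with 40 per arm, raw-mean power in step 2 runs from 0.04-0.06 (centred on the window) to 0.67-0.96 (centred on its edge).

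For Regularity, a general 20% fall is detected with about 69% power on the log scale against 38-51% for the flag at 40 per arm, and about 31% against 15-22% at 15 per arm. These figures assume a lognormal SD with log-SD 0.4 and a proportional effect across participants. If change is confined to people just over 60 min, the order reverses. The continuous measure should therefore stand beside the flag and not replace it.

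**What to change.** 1. Keep the 0-6 composite and its six flags as planned.
2. Add each participant's SD of sleep midpoint, log-transformed, as a continuous secondary outcome compared between the randomised groups. It comes from nightly tracker data already planned. Correct the bracket in Table 1's midpoint formula first: for onset 23:00 and wake 07:00 (31 on a running clock), the printed form gives 23 + (31 - 23/2) = 42.5, whereas 23 + (31 - 23)/2 = 27, that is 3am.
3. State that benefit or harm conclusions on Timing and Duration rest on Table 1's windows through the flag. As an optional supportive score, use minutes outside the window (0 if inside), analysed with a method suited to many zeros.
4. Report raw mean midpoint and minutes asleep descriptively only. Do not use distance from 3am or 7 hours.

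Cost: a few sentences and one or two derived variables, with no new data collection. The downside is one more secondary outcome to report.

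### The sleep-midpoint formula in Table 1 has a misplaced bracket: it gives wake time plus half of onset and would mis-score Timing and Regularity.

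*Combined protocol and SAP*

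**What the plan says.** The formula is in the Regularity row of Table 1 (Sleep Health Composite), under Specific Aim 1: "Standard deviation of sleep midpoint, which is calculated as [sleep onset + (wake time – sleep onset/2". The round and square brackets close immediately after the 2. A standard deviation below 60 minutes counts as good.

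The Timing row reads "Average sleep midpoint", with 2am to 4am as good, and has no formula of its own. Elsewhere under Specific Aim 1, sleep midpoint is listed among the FitBit markers but not defined. No rule is given for nights that cross midnight.

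On scoring, the text above the table says: "Each sleep health domain will be dichotomized using the cut-off points in Table 1 with 0 = poor sleep health and 1 = good sleep health". It continues: "The domains will be summed to create the composite sleep health score ranging from 0 - 6". The experimental design for Aim 1 places the Ru-SATED questionnaire among the measures tied to the study's primary objectives.

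**The concern.** A midpoint is onset plus half the interval from onset to wake. In the printed expression the division applies to onset alone. Because Timing borrows the same quantity, one misplaced bracket reaches two of the six domains. Each domain is scored 0 or 1 against a hard cut-off, so up to 2 of 6 points are exposed.

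These domains are also close to what the intervention tries to change. The video, and the text message for days 1 and 16, both teach regular sleep and wake times. A Timing score that is wrong for most ordinary sleepers cannot register improvement.

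**Working it through.** **Inputs.** From Table 1: the formula, the cut-offs (below 60 minutes; 2am to 4am) and 0/1 scoring. The plan gives no spread for onset or wake times, so the standard deviations and correlations below are assumptions. It states no worked midpoint to reproduce.

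**Algebra.** Let O be onset and W wake time.
- As printed: O + (W − O/2) = W + O/2.
- Midpoint: O + (W − O)/2 = (O + W)/2.

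**One night, 23:00 to 07:00 (true midpoint 03:00).**

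| Clock origin | O | W | W + O/2 | Clock time |
|---|---|---|---|---|
| Midnight within the night | −1 | 7 | 6.5 | 06:30 |
| Preceding noon | 11 | 19 | 24.5 | 12:30 |
| Preceding midnight | 23 | 31 | 42.5 | 18:30 |

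All three score poor on Timing. A real clock time cannot depend on where counting starts; this one does.

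**Timing, general case.** With true midpoint M and sleep span D, O = M − D/2 and W = M + D/2. Counted from midnight, the printed formula gives 1.5M + D/4.
- For M from 2 to 4 and D from 6 to 8 hours, the result runs from 3 + 1.5 = 4.5 (04:30) to 6 + 2 = 8 (08:00).
- Counting from noon adds 6 hours (10:30 to 14:00). Counting from the preceding midnight adds 12 (16:30 to 20:00).
- None of these values lies in 2am to 4am.
- With D = 7 and a midnight origin, the true midpoints scored good run from (2 − 1.75)/1.5 = 0.17 h to (4 − 1.75)/1.5 = 1.5 h, that is 00:10 to 01:30.

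**Timing, share of people.** Assume person means of 23:00 and 07:00, each with SD 1 h, correlation 0.4, counted from midnight.
- True midpoint: mean 3, SD √((1 + 1 + 0.8)/4) = 0.84 h. About 77% fall in 2am to 4am.
- As printed: mean 6.5, SD √(1 + 0.25 + 0.4) = 1.28 h. About 2.6% fall there.

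**Regularity.** With nightly SDs s_O and s_W and correlation ρ:
- SD as printed = √(s_W² + s_O²/4 + ρ s_O s_W)
- SD of midpoint = √((s_O² + s_W² + 2ρ s_O s_W)/4)
- Excess variance = 0.75 s_W² + 0.5 ρ s_O s_W

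| s_O = s_W (min) | ρ | Midpoint SD | SD as printed | Score changes? |
|---|---|---|---|---|
| 40 | 0.5 | 34.6 | 52.9 | No, both good |
| 50 | 0.3 | 40.3 | 62.2 | Yes |
| 60 | 0.3 | 48.4 | 74.7 | Yes |
| 60 | 0.5 | 52.0 | 79.4 | Yes |
| 75 | 0.5 | 65.0 | 99.2 | No, both poor |

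With equal SDs the ratio is 1.58 at ρ = 0 and 1.51 at ρ = 0.8. A score therefore changes when the true SD lies between about 60/1.58 = 38 (or 60/1.51 = 40) minutes and 60 minutes.

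With unequal SDs the inflation can be small. For s_O = 60, s_W = 20 and ρ = 0.3, the SDs are √1180 = 34 and √1660 = 41 minutes, both good.

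**Midnight.** Moving the bracket is not enough if raw clock hours are entered. A night from 23:00 to 07:00 gives (23 + 7)/2 = 15:00, and one from 00:00 to 07:00 gives (0 + 7)/2 = 03:30. The true midpoints, 03:00 and 03:30, differ by 30 minutes; the computed ones differ by 11.5 hours.

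**The case against.** The strongest reply is that this is a notation slip with obvious intent. The quantity is called a midpoint, the terms appear in the right order, and a 2am to 4am window makes sense only for a true midpoint. A careful programmer would correct it, and a typical Timing value of 06:30 or 18:30 would give the error away. Midpoint is derived after collection, so a late correction loses no data. The first-year primary outcomes are feasibility measures that do not use it. An error common to both arms would not favour either. The Regularity changes depend on assumed SDs. A stacked fraction in the source table could also have flattened into this string.

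Much of this stands. The harm arises only if the formula is coded literally, and the Regularity effect is confined to people near the cut-off. Damage in text conversion is possible but unlikely, because the expression is complete and its brackets balance; the sponsor's source file would settle it.

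Three parts do not stand. A Regularity SD of 75 minutes looks plausible, so nothing would prompt a programmer to question it. The shared error does not merely dilute an effect: with a 7 hour span counted from midnight, a participant whose true midpoint moves from 01:00 to 02:30 improves on Timing, yet the printed values are 1.5 + 1.75 = 3.25 h (03:15, good) and 3.75 + 1.75 = 5.5 h (05:30, poor). Finally, the plan leaves treatment effect for further assessment in years two and three, when the composite will matter.

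**Conclusion.** The concern holds. The printed formula is algebraically wrong, no correct version appears elsewhere in the plan, and it defines two of the six domains. That conclusion rests on no outside figure.

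The consequences are conditional on literal programming. Timing would then be scored poor for every sleeper with a true 2am to 4am midpoint and a 6 to 8 hour span, under each of the three clock origins tried. Some sleepers with earlier midpoints would be scored good if time is counted from midnight. The contrast of 77% with 2.6% depends on the assumed spread and correlation of person means. Regularity would be inflated whenever wake time varies and the correlation is not negative, but the 0/1 score changes only near 60 minutes. The loss of 2 points is the worst case for one participant, not the average.

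Because this is a stated scoring rule for a measure tied to the primary objectives, it should be corrected before any composite is computed.

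**What to change.** Replace the expression in the Regularity row with: sleep midpoint = sleep onset + (wake time − sleep onset)/2, with both times in minutes after a fixed reference before bedtime, such as noon or 18:00. State in the Timing row that the same midpoint is used.

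Add one test case for whoever programs the score. From noon, 23:00 is 660 minutes and 07:00 is 1140, so the midpoint is 660 + 480/2 = 900 minutes, or 03:00. On that scale the 2am to 4am window is 840 to 960 minutes.

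If the device export supplies a midpoint directly, the plan should say so and confirm that it follows this definition.

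The cost is one line in Table 1 and a cross-reference. Visits, data collection and sample size do not change. If scores have already been computed, they can be rederived from the nightly onset and wake times, provided those are kept.

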**Table 1: Sleep Health Composite**

[figure not shown]

**Figure 1: Study design for Specific Aim 1.**

**Specific Aim 2: Assess the ability of daily automated text messaging in CDOA to serve as an effective augmentation for sleep hygiene education.**

Rationale: Our second aim is to study the effectiveness of sending automated text messaging as an effective augmentation for sleep hygiene education in CDOA. With the promising short term results of a one-time sleep hygiene education session in young adults and the working adult population, we want to test if reinforcing the education daily through the use of a simple text message over the course of 4 weeks provides even greater and more sustainable results on changing people’s sleep behaviors. The expansion of smartphone technology combined with the abundance of services offering bulk messages to be sent out automatically provides an opportunity to reinforce the initial education with continual reminders of good sleep habits that an individual can practice over the course of 4-weeks. Given that 86% of adults over 50 now consistently use text messaging; it is safe to say this is an easy way to provide daily education and reminders on good sleep habits to this population.[28] If a new habit can be solidified during this timeframe, perhaps we will see long-term changes in sleep that will greatly improve overall health and wellness. For these reasons, we want to explore using automated text messaging as a supplement to our 30-minute educational video for sleep hygiene education.

Experimental design: Following anthropometric data collection and vital signs, as well as having the participants watch the sleep hygiene education video created by the research team, the participants will be randomly assigned to one of two groups (Figure 2). The intervention group will receive daily automated text messages scheduled for 8:00 pm every evening. The text messages will include a variety of sleep hygiene behavioral tips for the participant to try (Table 2). The participants will receive the text messages for a total of 4 weeks. The control group will not receive any intervention during this time frame. Following the 4 weeks, PI and student researcher(s) will meet again with the participants to collect the same data that was collected at the initial visit. Each participant will have a total of 2 sessions to complete with each session taking approximately 45-60 minutes to complete.

Sleep Hygiene Education Video Group

(n=15)

Sleep Hygiene Education Video Plus Daily  
Automated Text Messaging Group

(n=15)

